4.3.5.2 Presentations

The following summaries will be provided by actual treatment group for each ECG parameter:

- Number and percentages of participants with at least one markedly abnormal post-baseline observed value/change from baseline (for quantitative parameters; refer to Section 4.3.5.1)
- Listing of participants with at least one markedly abnormal observed value/change from baseline
- Shift from baseline in overall ECG interpretation to the worst post-baseline assessment; the hierarchy order of clinically significant abnormal, not clinically significant abnormal, and normal from worst abnormal to normal will be followed
- Listing of participants with at least one abnormal overall ECG interpretation, including the finding(s) for each participant

All individual measurements will be listed.

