1.3 Schedule of Activities

[Table 1](#) summarizes the SoA for the screening and treatment period for Arm A (AZD7442 Q3M).

[Table 2](#) summarizes the SoA for the screening and treatment period for Arm B (AZD7442 Q6M).

[Table 3](#) summarizes the SoA for the follow-up period for Arm A and Arm B.

[Table 4](#) summarizes the assessments to be conducted when Illness Visits are initiated for participants who are suspected to have COVID-19.

Participants who permanently discontinue IMP administration due to the premature termination of the study will remain in the study to complete visits/assessments (except those related to monitoring of IMP administration) for at least 6 months after their final dose of AZD7442.

- If participants receive their last study drug administration on Day 183 visit, they will complete Day 190, Day 212, and Day 274 (no dosing) visits, followed by an Early Discontinuation visit in place of the Day 365 visit.
- If participants receive their last study drug administration on Day 274 visit, they will complete Day 281, and Day 365 (no dosing) visits, followed by an Early Discontinuation visit in place of the Day 456 visit.
- If participants have already completed visit/assessments up to 6 months after the last IMP administration (i.e. Day 365), the early discontinuation visit will be scheduled as early as possible. However, if early discontinuation scheduling is within one month of last completed in person visit and required samples were collected per protocol, then no additional sample collection is required (with the exception of a urine pregnancy test for WOCBP, and if positive or indeterminant, serum pregnancy will be collected).
- If participants are completing an illness visit series, they will be followed until completion or until the Early Discontinuation visit.

Table 1 Schedule of Activities: Treatment Period – Arm A (AZD7442 Q3M)

Period	Screen ^a	Treatment (Days 1-456)													EoT	For details, see Section
Day (* = IMP dosing day)	-7 to 1	1*	8	29	92*	99	121	183*	190	212	274*	281	365*	372	456	
Week (Month)	-	-	1	4	13 (3M)	14	17 (4M)	26 (6M)	27	30 (7M)	39 (9M)	40	52 (12M)	53	65 (15M)	
Window (days)	-	-	± 3	± 5	± 7	± 3	± 5	± 7	± 3	± 5	± 7	± 3	± 7	± 3	± 15	
P = In-Person Visit RTM = Remote TM Visit ^m	P	P	RTM/ P ^m	P	P	RTM/ P ^m	P	P	RTM/ P ^m	P	P	RTM/ P ^m	P	RTM/ P ^m	P	
Procedure																
Informed consent	X															5.1
Informed assent for pediatric participants	X															5.1

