Assignment PID number	X															-
Demographics	X															-
Medical and surgical history	X															-
Smoking status and pack-history (pack history for current and former smokers)	X															-
Complete physical examination, including height and weight	X															8.2.1

Table 1 Schedule of Activities: Treatment Period – Arm A (AZD7442 Q3M)

Period	Screen ^a	Treatment (Days 1-456)													EoT	For details, see Section
Day (* = IMP dosing day)	-7 to 1	1*	8	29	92*	99	121	183*	190	212	274*	281	365*	372	456	
Week (Month)	-	-	1	4	13 (3M)	14	17 (4M)	26 (6M)	27	30 (7M)	39 (9M)	40	52 (12M)	53	65 (15M)	
Window (days)	-	-	± 3	± 5	± 7	± 3	± 5	± 7	± 3	± 5	± 7	± 3	± 7	± 3	± 15	
P = In-Person Visit RTM = Remote TM Visit ^m	P	P	RTM/ P ^m	P	P	RTM/ P ^m	P	P	RTM/ P ^m	P	P	RTM/ P ^m	P	RTM/ P ^m	P	
Targeted physical examination (predose on days of IMP administration) ⁿ		X		X	X		X	X		X	X		X		X	8.2.1
COVID-19 symptom screening	X															5.1, 5.2
Concomitant medications	←-----→														6.5	
Vital signs (including pulse oximetry) (pre and postdose on days of IMP administration) ^b	X	X ^b		X	X ^b		X	X ^b		X	X ^b		X ^b		X	8.2.2
12-lead ECG (postdose on days of IMP administration)	X	X			X			X			X		X		X	8.2.3

Table 1 Schedule of Activities: Treatment Period – Arm A (AZD7442 Q3M)

Period	Screen ^a	Treatment (Days 1-456)													EoT	For details, see Section
Day (* = IMP dosing day)	-7 to 1	1*	8	29	92*	99	121	183*	190	212	274*	281	365*	372	456	
Week (Month)	-	-	1	4	13 (3M)	14	17 (4M)	26 (6M)	27	30 (7M)	39 (9M)	40	52 (12M)	53	65 (15M)	
Window (days)	-	-	± 3	± 5	± 7	± 3	± 5	± 7	± 3	± 5	± 7	± 3	± 7	± 3	± 15	
P = In-Person Visit RTM = Remote TM Visit ^m	P	P	RTM/ P ^m	P	P	RTM/ P ^m	P	P	RTM/ P ^m	P	P	RTM/ P ^m	P	RTM/ P ^m	P	
Verify eligibility criteria	X	X														5.1, 5.2
Randomization (after verification of eligibility)		X														6.3
Blood samples																
Cardiac/thrombosis biomarkers (predose on days of IMP administration); participants will be instructed to fast for ≥ 8 hours prior to collection		X		X	X			X			X		X		X	8.2.4
Serum chemistry (predose on days of IMP administration)		X			X			X			X		X		X	8.2.4
Hematology (predose on days of IMP administration)		X			X			X			X		X		X	8.2.4

Table 1 Schedule of Activities: Treatment Period – Arm A (AZD7442 Q3M)

Period	Screen ^a	Treatment (Days 1-456)													EoT	For details, see Section
Day (* = IMP dosing day)	-7 to 1	1*	8	29	92*	99	121	183*	190	212	274*	281	365*	372	456	

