3.3.1 General Study Level Definitions

Reference start date and study day

Study Day will be calculated from the reference start date and will be used to show start/stop day of assessments and events. Reference start date is defined as the first day of the dose of IMP i.e., Day 1.

Study Day will be computed as follows:

- *Study Day = (Date of assessment/event – Date of first dose of IMP) + 1 if the date of the assessment/event is on or after the date of the first dose of IMP.*

- *Study Day = (Date of assessment/event – Date of first dose of IMP) if the date of the assessment/event is prior to the date of the first dose of IMP.*

In general, when the assessment/event date is partial or missing, Study Day and any corresponding durations will be displayed as missing in the listings.

For illness visits, an illness study day will be calculated. The reference start date is defined as the day of first illness assessment, i.e., illness visit Day 1. This will be calculated separately for each illness episode.

Illness Study Day will be computed as follows:

- *Illness Study Day = (Date of assessment/event – Date of illness visit Day 1) + 1.*

Baseline

In general, baseline is defined as the last non-missing measurement taken prior to the first dose of IMP. If the last non-missing measurement is taken at same date and time of the dose of IMP, this measurement will be considered baseline, with the exception of adverse events (AEs) and non-IMP medications commencing on the date and time of the dose of IMP, these assessments will be considered post-baseline.

Illness Visit baseline is defined as the first non-missing measurement taken on Illness Visit Day 1. If there is no non-missing measurement available on Illness Visit Day 1, Illness Visit baseline is considered as missing. For instances, where Illness Visit Day 1 occurs on the same day as a main study Visit, and Illness Visit Day 1 measurements are missing, then the measurements from the main study Visit will be used as Illness Visit baseline. Otherwise, if there is still no available measurement for Illness Visit Day 1, Illness Visit baseline is considered as missing.

Change from baseline will be calculated as (*post-baseline visit – baseline visit*).

Change from baseline for Illness Visits will be calculated as:

- *Change from baseline at Illness Visit Day 1 = Test value at Illness Visit Day 1 – Baseline value*

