Day 1, During Dose, 30 mins	1	>22 minutes 30 seconds post 1 st IMP dose time - ≤ 37 minutes 30 seconds minutes post 1 st IMP dose time
Day 1, During Dose, 45 mins	1	>37 minutes 30 seconds post 1 st IMP dose time - ≤ 52 minutes 30 seconds post 1 st IMP dose time
Day 1, During Dose, 60 mins	1	> 52 minutes 30 seconds post 1 st IMP dose time - ≤ 67 minutes 30 seconds post 1 st IMP dose time
Day 1, Post-dose	1	1, >67 minutes 30 seconds post 1 st IMP dose time
Day 29	29	2 - 60
Day 92	92	61 - 137
Day 183, Pre-dose	183	138 – 197, ≤ 2 nd IMP dose time
Day 183, Post-dose	183	138 – 197, > 2 nd IMP dose time

Visit	Day Relative to First Dose	Visit Window (Study Day)
Day 212	212	198 - 242
Day 274	274	243 - 319
Day 365, Pre-dose	365	320 – 410, \leq 3 rd IMP dose time
Day 365, Post-dose	365	320 – 410, $>$ 3 rd IMP dose time
Day 456	456	411 - 592
Day 729 (Follow-up)	729	\geq 593

Table 8: Analysis windows for ECG

Arm A

Visit	Day Relative to First Dose	Visit Window (Study Day)
Screening	<1	<1
Day 1	1	1
Day 92	92	2 - 137
Day 183	183	138 - 228
Day 274	274	229 - 319
Day 365	365	320 - 410
Day 456	456	\geq 411

Arm B

Visit	Day Relative to First Dose	Visit Window (Study Day)
Screening	<1	<1
Day 1	1	1
Day 183	183	2 - 273
Day 365	365	274 - 410
Day 456	456	\geq 411

Table 9: Analysis windows for immunogenicity, PD, PK, coagulation, serum sample for exploratory assessments (Illness visit schedule)

Visit	Day Relative to Illness	Visit Window (Study Day)
Illness Day 1	≤ 1	≤ 1
Illness Day 14	14	≥ 2

Table 10: Analysis windows for COVID-19 symptom assessment, SARS-CoV-2 RT-PCR sequencing NP swab, and vital signs (for Confirmed Illness visit schedule)

Visit	Day Relative to Illness	Visit Window (Study Day)
Illness Day 1	≤ 1	≤ 1

Visit	Day Relative to Illness	Visit Window (Study Day)
Illness Day 5	5	2- 5
Illness Day 7	7	6 - 10
Illness Day 14	14	≥11 (for Vital signs) 11 – 20 (for Covid-19 symptoms)
Illness Day 28	28	21 – 58 (for Covid-19 symptoms)
Illness Day 90	90	≥59 (for Covid-19 symptoms)

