4.3.5 Electrocardiogram

4.3.5.1 Definitions and Derivations

The following ECG parameters will be measured for this study as per the schedule of events (see Protocol Section 1.3):

- PR interval (msec)
- QRS duration (msec)
- QT interval (msec)
- QTc interval (msec)
- QTcB interval (msec)
- QTcF interval (msec)
- RR interval (msec)
- ECG mean heart rate (beats/min)

The overall interpretation of the ECG results will be classified as normal, abnormal not clinically significant, or clinically significant abnormal by the investigator.

Additionally, markedly abnormal quantitative ECG parameters will be identified in accordance with the following predefined markedly abnormal criteria:

- Observed values for QTc, QTcF, and QTcB intervals will be classified as:
 - > 450
 - > 480
 - > 500 msec
- Change from baseline for QTc, QTcF, and QTcB intervals will be classified as:
 - > 30 msec increase from baseline
 - > 60 msec increase from baseline

It is to be noted that the previous categories are not mutually exclusive, but cumulative. For example, if a participant's worst post-baseline QTc post-baseline observed value is 490 mmHg, then this participant will be reported once under QTc > 450 msec and once under QTc > 480 msec.

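### By-arm ECG tables count any or worst post-baseline value, but Arm A is scheduled for more ECGs than Arm B, which tilts the expected contrast against Arm A

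*SAP*

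**What the plan says.** SAP 4.3.5.2 lists two ECG tables by actual treatment group. The first is "Number and percentages of participants with at least one markedly abnormal post-baseline observed value/change from baseline". The second is "Shift from baseline in overall ECG interpretation to the worst post-baseline assessment". The rest of the section is listings, including all individual measurements.

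SAP 4.3.5.1 defines the criteria: "Observed values for QTc, QTcF, and QTcB intervals will be classified as" above 450, 480 and 500 ms, with increases from baseline above 30 and 60 ms.

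ECG timing follows dosing. Protocol Tables 1 and 2 carry the same row, "12-lead ECG (postdose on days of IMP administration", but the arms are dosed on different days. SAP 3.3.2 repeats the difference in "Table 8: Analysis windows for ECG": Days 1, 92, 183, 274, 365 and 456 for Arm A, and Days 1, 183, 365 and 456 for Arm B.

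For participants last dosed on Day 183, Protocol 1.3 says "they will complete Day 190, Day 212, and Day 274 (no dosing) visits, followed by an Early Discontinuation visit", which takes the place of Day 365. Protocol Table 3 includes an ECG at Early Discontinuation, and SAP 3.3.3 brings early discontinuation measurements into the summaries.

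**The concern.** The chance that a participant has at least one abnormal ECG, or a worse worst ECG, grows with the number of recordings unless repeat recordings in one person always agree. If one arm is recorded more often, the two percentages do not estimate the same quantity.

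Nothing in SAP 4.3.5.2 offsets this. Laboratory values and vital signs each have a summary of observed value and change from baseline by visit (SAP 4.3.3.2 and 4.3.4.2); ECGs do not. Neither ECG table is limited to common visits or shows how many ECGs lie behind each percentage. The exposure-adjusted rate in SAP 4.3.2.1 covers adverse events and uses follow-up time.

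Safety is a primary objective and the regimens will be read side by side. Under Protocol 8.3.6, an ECG deterioration becomes an adverse event only if it is serious, leads to IMP discontinuation or is judged clinically relevant. Many QTc outliers would therefore appear only in these tables and the listings. A reader could take a schedule effect for a regimen effect.

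**Working it through.** **Formula check.** The plan gives no ECG figure. Its only at-least-one figure is the sample-size statement (3% AE rate, 100 participants, 95%): 1 − 0.97^100 = 0.952, which reproduces. The same expression governs repeated ECGs within a person when they are independent.

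**Counting post-baseline ECGs.** SAP 3.3.1: "baseline is defined as the last non-missing measurement taken prior to the first dose of IMP". The Day 1 ECG is postdose, so it is post-baseline and screening supplies the baseline.

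| Path | Arm A | Arm B |
|---|---|---|
| Full schedule | 1, 92, 183, 274, 365, 456 = 6 | 1, 183, 365, 456 = 4 |
| Last dose Day 183 in both arms | 1, 92, 183, 274, Early Discontinuation = 5 | 1, 183, Early Discontinuation = 3 |
| Arm A last dose Day 274, Arm B last dose Day 183 | 1, 92, 183, 274, 365, Early Discontinuation = 6 | 3 |
| Day 365 already completed, last dose Day 183 | 1, 92, 183, 274, 365, Early Discontinuation = 6 | 1, 183, 365, Early Discontinuation = 4 |

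The counts treat the ECG at an undosed visit as still done. Only assessments related to monitoring of IMP administration (Protocol 8.2.5) are dropped, and ECG has its own section (8.2.3). If the undosed Day 274 ECG were dropped, the second row would be 4 v 3.

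**Independent ECGs (upper bound).** With per-ECG probability p = 5% in both arms, 1 − 0.95^m gives 14.3% (m = 3), 18.5% (4), 22.6% (5) and 26.5% (6).

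**Correlated QTc.** Assumptions: normal QTc, the same in both arms, mean μ = 415-425 ms, SD σ = 22 ms, within-person correlation r = 0.5-0.7. The documents give none of these. For m ECGs:

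- any value above c: 1 − ∫ φ(u) Φ[(c − μ − σ√r·u) / (σ√(1−r))]^m du
- any increase above d, with s = σ√(1−r): 1 − ∫ φ(b) Φ[(d + s·b)/s]^m db

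Hand check at m = 1: above 450 ms with μ = 415 is 1 − Φ(35/22) = 5.6%. An increase above 30 ms with r = 0.5 has SD 22·√0.5·√2 = 22, so 1 − Φ(30/22) = 8.6%.

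Expected percentages by number of ECGs (gaps in points, taken before rounding):

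| Criterion and inputs | 3 | 4 | 5 | 6 | 6 v 4 | 5 v 3 | 6 v 3 |
|---|---|---|---|---|---|---|---|
| >450, μ 415, r 0.7 | 11.3 | 13.2 | 14.8 | 16.2 | 2.9 | 3.5 | 4.8 |
| >450, μ 425, r 0.5 | 26.9 | 31.6 | 35.3 | 38.4 | 6.9 | 8.4 | 11.5 |
| >30, r 0.7 | 9.5 | 11.6 | 13.5 | 15.2 | 3.6 | 4.0 | 5.7 |
| >30, r 0.5 | 19.2 | 22.9 | 26.0 | 28.7 | 5.8 | 6.8 | 9.5 |

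For the other three criteria over the same inputs, the 6 v 3 gap is 0.3-1.3 points (>480), below 0.1 (>500) and 0.1-0.7 (>60). At r = 0.85 the >30 ms gap falls to 0.9 points (6 v 4) or 1.3 (6 v 3).

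**Chance of the tilt showing.** With 100 per arm, p = 5% and an exchangeable latent-normal correlation of 0.5, Arm A's expected percentage is 18.6% against 14.4% (6 v 4) or 11.8% (6 v 3). Arm A's count then exceeds Arm B's with probability 0.76 or 0.89. In the 6 v 4 case Arm B's count is the higher one with probability 0.19.

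**Effect of the fix.** Restricting to Days 1, 183, 365 and 456 gives 4 v 4 on the full schedule. It gives 3 v 3 when both arms are last dosed on Day 183 and the Early Discontinuation ECG takes the Day 365 slot. The ratio is then 1.00 for every p and r.

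**The case against.** The case against is mainly about size and consequence, and much of it stands.

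- Three of the five QTc criteria barely move. A reader might infer that every ECG table is distorted by many points; the calculation supports that only for >450 and >30 ms, and only under assumed inputs. High within-person correlation shrinks the gap further.
- A reader might infer that Arm A has twice as many ECGs. As planned the ratio is 6/4 = 1.5. Two to one arises on the path comparing Arm A last dosed on Day 274 with Arm B last dosed on Day 183, and those groups also differ in follow-up.
- A reader might infer that Arm A is bound to look worse. The excess is an expectation, not a certainty in any one sample.
- A reader might link these tables to the product's cardiac risk. Protocol 2.3.1 raises cardiac ischemia, cardiac failure and thrombotic events, and names no QT signal. Those events are analysed through AESIs, adjudicated cardiovascular events and the serious-event tables in SAP 4.3.2.2, and cardiac biomarkers are drawn at the same visits in both arms.
- No hypothesis is tested, and every ECG is listed, so anyone with the listings can recompute.

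The general provision in SAP 3.3 for summaries by treatment and visit when applicable does not answer the point. Section 4.3.5.2 lists no by-visit ECG table, and the any-occurrence and worst-value tables would be unchanged by one.

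**Conclusion.** The point holds as a modest analysis flaw. The unequal counts are plain in Protocol Tables 1 and 2 and SAP Table 8, and the two planned ECG statistics increase with the count. With equal true QTc, Arm A's expected percentages exceed Arm B's. On the full 6 v 4 schedule the excess is about 3-7 points for >450 ms and 4-6 points for >30 ms. On the 6 v 3 path it is about 5-12 and 6-9.5 points. For >480, >500 and >60 ms it is below 1.5 points.

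The direction rests only on repeat ECGs in a person not agreeing perfectly. The size rests on the assumed mean, SD and correlation. The documents do not support reading this as a threat to the trial's safety conclusions: it affects descriptive tables in a supporting safety domain, and the data needed to correct it are collected and listed.

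**What to change.** In SAP 4.3.5.2:

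1. Add a by-arm version of both tables restricted to ECG visits scheduled in both arms: Day 1 postdose, Day 183, Day 365 and Day 456. Assign the Early Discontinuation ECG to the visit it replaces, and state a rule for one that replaces no named visit.
2. Use the same windows in both arms for this version. Table 8 now gives Day 183 as 138-228 in Arm A and 2-273 in Arm B, and Day 365 as 320-410 and 274-410. Applying Arm A's windows to both would do.
3. Add observed and change-from-baseline ECG values by visit, as for laboratory values and vital signs.
4. Keep the all-ECG tables and show the number of post-baseline ECGs per participant by arm.

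The cost is a short SAP paragraph, a record flag and a few extra tables; no new data are needed. The common-visit table leaves out Arm A's Day 92 and Day 274 ECGs, which stay in the all-ECG tables and listings.

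One imbalance remains. Arm A participants last dosed on Day 274 contribute 4 common visits (Days 1, 183, 365 and Early Discontinuation in the Day 456 slot), while Arm B participants last dosed on Day 183 contribute 3. The by-visit summary and the displayed counts let the reader see this.

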4.3.6 Other Safety Assessments

4.3.6.1 Physical Examination

Physical examinations (completed and targeted) will be conducted as per the schedule of events (refer to Protocol Section 1.3). Clinically significant abnormal findings at screening

will be recorded in the Medical History, while clinically significant abnormal findings following vaccination will be recorded as AEs.

5 INTERIM ANALYSIS

No interim analysis is planned for this study.

7 APPENDIX

A 1 Partial Date Conventions

Algorithm for Prior / Concomitant Medications

START DATE	STOP DATE	ACTION
Known	Known or ongoing	If medication stop date < date of first dose of IMP, assign as prior; If medication start date < date of first dose of IMP and medication stop date ≥ date of first dose of IMP, assign as concomitant; If date of first dose of IMP ≤ medication start date, assign as concomitant.
	Partial	If known components of medication stop date show that medication stopped before date of first dose of IMP, assign as prior; If medication start date < date of first dose of IMP and (known components of medication stop date show that medication stopped on or after date of first dose of IMP), assign as concomitant; If date of first dose of IMP ≤ medication start date, assign as concomitant.

START DATE	STOP DATE	ACTION
	Missing, not ongoing	If medication stop date is missing, then it can never be assigned as prior only; If medication start date < date of first dose of IMP, assign as concomitant; If date of first dose of IMP ≤ medication start date, assign as concomitant.
Partial	Known or ongoing	If medication stop date < date of first dose of IMP, assign as prior; If (known components of medication start date show that medication started before date of first dose of IMP) and (medication stop date ≥ date of first dose of IMP), assign as concomitant; If known components of medication start date show that medication started on or after date of first dose of IMP, assign as concomitant.
	Partial	If known components of medication stop date show that medication stopped before date of first dose of IMP, assign as prior; If (known components of medication start date show that medication started before date of first dose of IMP) and (known components of medication stop date show that medication stopped on or after date of first dose of IMP), assign as concomitant; If known components of medication start date show that medication started on or after date of first dose of IMP, assign as concomitant.
	Missing, not ongoing	Cannot be assigned as prior only; If known components of medication start date show that medication started before study drug start date, assign as concomitant; If known components of medication start date show that medication started on or after date of first dose of IMP, assign as concomitant.
Missing	Known or ongoing	If medication stop date < date of first dose of IMP, assign as prior; If medication stop date ≥ date of first dose of IMP, assign as concomitant.
	Partial	If known components of medication stop date show that medication stopped before date of first dose of IMP, assign as prior; If known components of medication stop date show that medication stopped on or after date of first dose of IMP, assign as concomitant.
	Missing, not ongoing	Assign as concomitant.

A 2 CTCAE Toxicity Grade, Version 5.0

CTCAE Term	Laboratory test	Grade 1	Grade 2	Grade 3	Grade 4
Anemia	Hemoglobin (g/dL)	<LLN - 10.0	<10.0 - 8.0	<8.0	-
Eosinophilia ²	Absolute eosinophils	>ULN and >baseline	-	-	-
Leukocytosis	White blood cells (x 10E9/L)	-	-	>100	-
Cardiac troponin I increased	Troponin I (high sensitivity) ng/L	> 19.8 - <100 (males) >13.6 - <100 (females)	-	>= 100	-

CTCAE Term	Laboratory test	Grade 1	Grade 2	Grade 3	Grade 4
Activated partial thromboplastin (aPTT) time prolonged	aPTT (sec)	>ULN - 1.5 x ULN	>1.5 - 2.5 x ULN	>2.5 x ULN	-
Alanine aminotransferase (ALT) increased ¹	ALT (U/L)	>ULN - 3.0 x ULN if baseline was normal; 1.5 - 3.0 x baseline if baseline was abnormal	>3.0 - 5.0 x ULN if baseline was normal; >3.0 - 5.0 x baseline if baseline was abnormal	>5.0 - 20.0 x ULN if baseline was normal; >5.0 - 20.0 x baseline if baseline was abnormal	>20.0 x ULN if baseline was normal; >20.0 x baseline if baseline was abnormal
Alkaline phosphatase (ALP) increased ¹	ALP (U/L)	>ULN - 2.5 x ULN if baseline was normal; 2.0 - 2.5 x baseline if baseline was abnormal	>2.5 - 5.0 x ULN if baseline was normal; >2.5 - 5.0 x baseline if baseline was abnormal	>5.0 - 20.0 x ULN if baseline was normal; >5.0 - 20.0 x baseline if baseline was abnormal	>20.0 x ULN if baseline was normal; >20.0 x baseline if baseline was abnormal
Aspartate aminotransferase (AST) increased ¹	AST (U/L)	>ULN - 3.0 x ULN if baseline was normal; 1.5 - 3.0 x baseline if	>3.0 - 5.0 x ULN if baseline was normal; >3.0 - 5.0 x baseline if	>5.0 - 20.0 x ULN if baseline was normal; >5.0 - 20.0 x baseline if	>20.0 x ULN if baseline was normal; >20.0 x baseline if

CTCAE Term	Laboratory test	Grade 1	Grade 2	Grade 3	Grade 4
		baseline was abnormal	baseline was abnormal	baseline was abnormal	baseline was abnormal
Blood bilirubin increased ¹	Total bilirubin (µmol/L)	>ULN - 1.5 x ULN if baseline was normal; > 1.0 - 1.5 x baseline if baseline was abnormal	>1.5 - 3.0 x ULN if baseline was normal; >1.5 - 3.0 x baseline if baseline was abnormal	>3.0 - 10.0 x ULN if baseline was normal; >3.0 - 10.0 x baseline if baseline was abnormal	>10.0 x ULN if baseline was normal; >10.0 x baseline if baseline was abnormal
Cholesterol high	Cholesterol (mmol/L)	>ULN - 7.75	>7.75 - 10.34	>10.34 - 12.92	>12.92
Creatine phosphokinase (CPK) increased	Creatine kinase (U/L)	>ULN - 2.5 x ULN	>2.5 x ULN - 5 x ULN	>5 x ULN - 10 x ULN	>10 x ULN
Creatinine increased ²	Creatinine	>ULN - 1.5 x ULN	>1.5 - 3.0 x baseline; >1.5 - 3.0 x ULN	>3.0 x baseline; >3.0 - 6.0 x ULN	>6.0 x ULN

CTCAE Term	Laboratory test	Grade 1	Grade 2	Grade 3	Grade 4
Gamma glutamyl transferase (GGT) increased ¹	GGT (U/L)	>ULN - 2.5 x ULN if baseline was normal; 2.0 - 2.5 x baseline if baseline was abnormal	>2.5 - 5.0 x ULN if baseline was normal; >2.5 - 5.0 x baseline if baseline was abnormal	>5.0 - 20.0 x ULN if baseline was normal; >5.0 - 20.0 x baseline if baseline was abnormal	>20.0 x ULN if baseline was normal; >20.0 x baseline if baseline was abnormal
Hemoglobin increased	Hemoglobin (g/dL)	Increase from ULN in >0 - 2	Increase from ULN in >2 - 4	Increase from ULN in >4	-
International normalized ratio (INR) increased ³	INR	>1.2 – 1.5	>1.5 – 2.5	>2.5	-
Lymphocyte count decreased	Absolute lymphocytes count (x 10E9/L)	<LLN – 0.8	<0.8 – 0.5	<0.5 – 0.2	<0.2
Lymphocyte count increased	Absolute lymphocytes count (x 10E9/L)	-	>4 – 20	>20	-
Neutrophil count decreased	Absolute neutrophils count (x 10E9/L)	<LLN – 1.5	<1.5 – 1.0	<1.0 – 0.5	<0.5

CTCAE Term	Laboratory test	Grade 1	Grade 2	Grade 3	Grade 4
Platelet count decreased	Platelet count (x10E9/L)	<LLN – 75.0	<75.0 – 50.0	<50.0 – 25.0	<25.0
White blood cell (WBC) decreased	WBC (x 10E9/L)	<LLN – 3.0	<3.0 – 2.0	<2.0 – 1.0	<1.0
Hypercalcemia ⁴	Corrected serum calcium (mmol/L)	>ULN – 2.9	>2.9 – 3.1	>3.1 – 3.4	>3.4
Hyperkalemia	Potassium (mmol/L)	>ULN – 5.5	>5.5 – 6.0	>6.0 – 7.0	>7.0
Hypernatremia	Sodium (mmol/L)	>ULN - 150	>150 - 155	>155 - 160	>160
Hypoalbuminemia	Albumin (g/dL)	<LLN - 3	<3 - 2	<2	-
Hypocalcemia ⁴	Corrected serum calcium (mmol/L)	<LLN - 2.0	<2.0 – 1.75	<1.75 – 1.5	<1.5

CTCAE Term	Laboratory test	Grade 1	Grade 2	Grade 3	Grade 4
Hypoglycemia	Glucose (mg/dL)	<LLN - 55	<55 - 40	<40 - 30	<30
Hypokalemia	Potassium (mmol/L)	-	<LLN - 3.0	<3.0 - 2.5	<2.5
Hyponatremia	Sodium (mmol/L)	<LLN - 130	125-129	120-124	<120
Chronic kidney disease	Estimated glomerular filtration rate (eGFR) (ml/min/1.73m ²)	<LLN - 60	59 - 30	29 - 15	<15
Proteinuria	Urine protein	1+ proteinuria	Adult: 2+ and 3+ proteinuria	Adult: 4+ proteinuria	-

¹ Baseline grades, or post-baseline grades where no baseline visit available, follow the criteria defined for normal baseline results.

² Baseline grades, or post-baseline grades where no baseline visit available, do not follow criteria based on baseline results.

³ Derived only for participants not receiving anticoagulation medication.

⁴ Corrected serum calcium (mmol/L) derived $(0.02 * (40 \text{ g/L} - \text{albumin g/L})) + \text{serum calcium (mmol/L)}$.

Additional laboratory test may be collected if clinically indicated, at the discretion of the Investigator.

Source: https://ctep.cancer.gov/protocolDevelopment/electronic_applications/ctc.htm#ctc_50

A 3 Clinical Abnormalities: Vital Signs

Vital Signs Parameter	Vital Signs Grade			
	Mild (Grade 1)	Moderate (Grade 2)	Severe (Grade 3)	Potentially Life Threatening (Grade 4)
Fever (°C) (°F)	37.9-38.4	38.5-38.9	39.0-40	> 40
	100.1-101.1	101.2-102.0	102.1-104	> 104
Tachycardia (beats/minute)	101-115	116- 130	> 130	NA
Bradycardia (beats/minute) c	50-54	45-49	< 45	NA
Hypertension; systolic (mmHg)	141-150	151-155	> 155	NA
Hypertension; diastolic (mmHg)	91-95	96-100	> 100	NA
Hypotension; systolic (mmHg)	85-89	80-84	< 80	NA
Respiratory rate (breaths/minute)	17-20	21-25	> 25	NA

Hg = mercury. NA = not applicable.

Source: <https://www.fda.gov/media/73679/download>

A 4 Standardized MedDRA Query: Embolic and Thrombotic Events

It includes 3 sub standardized MedDRA queries:

- Embolic and thrombotic events, arterial (SMQ)
- Embolic and thrombotic events, venous (SMQ)
- Embolic and thrombotic events, vessel type unspecified and mixed arterial and venous (SMQ)

SIGNATURE PAGE

This is a representation of an electronic record that was signed electronically and this page is the manifestation of the electronic signature

Document Name: d8850c00010-sap-ed-2		
Document Title:	D8850C00010 Statistical Analysis Plan Edition 2	
Document ID:	Doc ID-004935358	
Version Label:	3.0 CURRENT LATEST APPROVED	
Server Date (dd-MMM-yyyy HH:mm 'UTC'Z)	Signed by	Meaning of Signature
24-Nov-2023 15:35 UTC	PPD [REDACTED] CYTEL	Author Approval
24-Nov-2023 15:13 UTC	PPD [REDACTED] (CLINCHOICE INC)	Content Approval
27-Nov-2023 08:21 UTC	PPD [REDACTED]	Author Approval

